8.5.1 Laboratory assessments for efficacy

8.5.1.1 Thrombin generation

The Thrombin Generation Assay (TGA) will be performed at all visits, except visit 3.

The TGA is included as an exploratory PD assessment.

The generation of thrombin is a fundamental part of the haemostatic system, and is a key measurable parameter of the formation of a clot under bleeding or thrombotic conditions. The thrombin burst is crucial for the formation of a stable fibrin clot.

The Calibrated Automated Thrombogram (CAT) method (used by Thrombinoscope BV) will be used to measure thrombin generation (TG). This method uses a slow acting fluorogenic substrate that allows continuous measurement of thrombin generation in double centrifuged citrated plasma.

In this assay set-up thrombin generation is initiated by low-dose tissue factor that is combined with phospholipid. The result is obtained by comparison to a constant known thrombin activity in a parallel non tissue factor initiated sample. The assay has been validated fit-for-purpose.

The thrombin generation endpoints are defined, but not limited to,

- The Endogenous Thrombin Potential (ETP) – the area under the curve
- Peak thrombin generation
- Velocity Index

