a	Concizumab administration is performed at home except for visit 2 where concizumab administration will take place at the trial site.
b	The duration of the visits will last according to patient's individual training need on concizumab administration, NovoPen®4, eDiary training etc. Visit 3 will be a phone call to the patient.
c	For patients being dose escalated a phone call is recommended 1 week after first new dose of concizumab.
d	Daily dosing preferably at the same time in the morning.
e	Evaluation of laboratory results obtained from samples taken at screening.
f	Bleeding episodes occurring between visit 1 and visit 2 or at site should be registered in the eCRF. All bleeding episodes except for severe occurring after visit 2 at home should be registered in the eDiary. Severe bleeding episodes must be registered in the eCRF.
g	Turoctocog alfa will be given to treat breakthrough bleeding episodes either in the clinic or at home.
h	At visit 9 and 16 all blood samples should be collected pre-dose. Patients must not treat themselves with concizumab until sampling has been performed.
i	Only body weight should be measured.
j	Vital signs should be evaluated before and after trial drug administration at visit 2.
k	Sampling for FVIII activity at screening should be postponed if the patient has received FVIII within 96 hours and medical records documenting the severity of haemophilia are not available.
l	FVIII activity and FVIII inhibitor tests should only be collected if reduced effect of turoctocog alfa or FVIII inhibitor development is suspected.
m	In case of clinical signs of e.g. hypersensitivity reactions or immune related events are seen, additional samples for ADAs may be taken. All antibody samples from the affected patient will be analysed on an ongoing basis. If antibodies are detected additional samples will be taken and stored for characterisation of the antibodies.
n	Only dispensing of turoctocog alfa and sodium chloride.
o	The trial patient must be in a non-bleeding state at the time of the first trial product administration (TPA), and should not have received any haemostatic drug (e.g. FVIII) for prophylaxis or treatment of a bleeding episode within a period of 48 hours prior to first TPA.

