8.1.7 Visit 1 (Screening part)

Informed consent must be obtained before any trial related activity, see Section [18.2](#).

In cases where a patient's baseline FVIII level is not documented in medical records, sampling for FVIII activity at screening should be postponed if the patient has received FVIII within 96 hours. Screening can take place between 14 to 21 days prior to planned enrolment day (visit 2).

All assessments to be performed at screening are listed in [Table 2-1](#), see Section [2](#).

Apart from informed consent patients will be asked to complete the ePRO questionnaires before any other trial related activities are performed according to Section [8.6](#);

- Hemo-TEM,
- VERITAS-Pro[®] or VERITAS-PRN[®]

Assessment results from physical examination, body measurements, as well as measurements of vital signs, urinalysis electrocardiogram (ECG) and details of any contemporary adverse events must be entered into the eCRF.

A screening confirmation call must be performed in the IWRS, at the day of the visit.

The investigator must review all information obtained from the screening procedures. If a patient does not meet all inclusion criteria or meets one or more of the exclusion criteria for the trial the patient does not qualify to be enrolled.

Patients will be provided with turoctocog alfa (rFVIII) trial injection kits and directions for use (DFU) to cover the potential FVIII treatment in the screening part of the trial and investigator will ensure that the patients are capable of treating themselves with rFVIII (turoctocog alfa). Patients on any previous FVIII prophylaxis can continue with this treatment until 48 hours before visit 2.

Dispensing of rFVIII (turoctocog alfa) should be performed in the IWRS

For bleeding episodes that occur in the period from Screening visit (Visit1) to enrolment visit (Visit 2) information about the bleeding episode is to be entered in the eCRF at visit 2.

The patient should be instructed to call the site if any bleeding episodes, questions or issues arise after he has left the site.

Protocol
Trial ID:NN7415-4255
UTN:U1111-1179-3872
EudraCT no.:2016-000614-29

~~CONFIDENTIAL~~

Date:	05 May 2017	Novo Nordisk
Version:	2	
Status:	Final	
Page:	45 of 124	

8.1.8 Training of patients visit 1 and visit 2

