8.1.9 Treatment period - Main part

8.1.9.1 Visit 2 (Assessment, 1st concizumab treatment at site)

Visit 2 should be scheduled 14 to 21 days after visit 1. The date of visit 2 will be considered as trial day 1.

Before any concizumab administration it is important to verify the in/exclusion criteria again and review central laboratory test results from screening.

The patient must be in a non-bleeding state at the time of first administration with concizumab and should not have received any FVIII treatment for prophylaxis or for treatment of a bleeding episode within a period of 48 hours prior to dosing.

Patients will be asked to complete the ePRO questionnaires before any other trial related activities are performed according to section [8.6.1](#);

- Hemo-TEM,
- SF-36v2,
- SDS,
- TSQM,
- SIAQ-ISRQ

All protocol assessments must be performed before 1st administration of concizumab. Vital signs must be assessed both before and after concizumab administration.

Assessment results from concomitant medication, vital signs, Body measurements (weight only) and details of adverse events must be entered into the eCRF.

At this, the 1st treatment visit, the allocated dose of concizumab will be given. Concizumab will be administered at the trial site supervised by medically trained trial staff.

Protocol
 Trial ID:NN7415-4255
 UTN:U1111-1179-3872
 EudraCT no.:2016-000614-29

~~CONFIDENTIAL~~

Date: 05 May 2017
 Version: 2
 Status: Final
 Page: 46 of 124

Novo Nordisk

The time point at which the completion of the first dose takes place corresponds to Time on treatment = 0 and must be recorded in the eCRF.

The patient must be observed at the trial site for at least 2 hours after the administration of the first dose of concizumab.

In order to determine the correct amount of the patient's daily dose of concizumab, until next scheduled visit, investigator will consult the dosing-table in the TMM on basis of the patient's current body weight.

Investigator will communicate any the daily dose of concizumab to the patient and record the dose for the coming home treatment period in the eCRF.

Prior to the first dose a dispensing call must be performed in the IWRS.

At the visit the patient will be provided with trial product (concizumab and if necessary rFVIII (turoctocog alfa)) and injection kits as well as an eDiary device to be able to conduct and report home treatment until the next scheduled visit.

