17.5 Additional analyses

An additional evaluation of the primary endpoint will be made, including actual concizumab dose level as *additional factor in the primary analysis model specified above*. Point estimates and 95% confidence interval will be provided for the ABR at the different dose levels of concizumab (0.15, 0.20 and 0.25 mg/kg). Furthermore, an analysis with individual steady state PK/PD assessments included as covariates in the negative *binomial regression model as specified for the primary analysis* will be performed in order to evaluate possible associations between PK/PD and ABR that potentially could guide dose-selection. The referred steady-state PK/PD assessments comprise the concizumab trough level, maximum plasma concentration (C_{max}) of concizumab, TFPI value prior to the last s.c. dose administration, peak thrombin generation (nM), Endogenous thrombin potential (nM*min) and velocity index (nM/min).

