17.6.2 Supportive secondary safety endpoints

- Number of treatment-emergent adverse events (TEAEs) during at least 24 weeks from treatment onset
- Number of TEAEs during 76 weeks from treatment onset.
- Occurrence of anti-concizumab antibodies during at least 24 weeks from treatment onset.
- Occurrence of anti-concizumab antibodies during 76 weeks from treatment onset.
- Change from baseline of fibrinogen during 24 weeks from treatment onset.
- Change from baseline of fibrinogen during 76 weeks from treatment onset.

Protocol
 Trial ID:NN7415-4255
 UTN:U1111-1179-3872
 EudraCT no.:2016-000614-29

~~CONFIDENTIAL~~

Date: 05 May 2017
 Version: 2
 Status: Final
 Page: 103 of 124

Novo Nordisk

- Change from baseline of D-dimer during 24 weeks from treatment onset.
- Change from baseline of D-dimer during 76 weeks from treatment onset
- Change from baseline of prothrombin fragment 1 + 2 (F1 + 2) during 24 weeks from treatment onset.
- Change from baseline of F1 + 2 during 76 weeks from treatment onset.
- Change from baseline of prothrombin time (PT) during 24 weeks from treatment onset.
- Change from baseline of PT during 76 weeks from treatment onset.
- Change from baseline of activated partial thromboplastin time (APTT) during 24 weeks from treatment onset.
- Change from baseline of APTT during 76 weeks from treatment onset.
- Change from baseline of antithrombin (AT) during 24 weeks from treatment onset.
- Change from baseline of AT 76 weeks from treatment onset.

Adverse Events will be coded using the most recent version of Medical Dictionary for Regulatory Activities (MedDRA) coding.

A Treatment Emergent Adverse Event (TEAE) is defined as an event that has onset from the first exposure to treatment until the last visit in the trial. Treatment-emergent adverse event endpoints will be summarised by system organ class, preferred term, seriousness, severity and relation to trial product. All Adverse events will further be listed.

Frequency of binding anti-concizumab antibodies will be listed and summarised by time frame according to the two endpoint definitions.

All laboratory safety endpoints will be plotted by time, both as absolute values and change from baseline. Laboratory safety endpoints will further be summarised and listed.

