17.6.4 Supportive secondary pharmacodynamic endpoints

Free TFPI concentration:

- Value prior to the last dose administration at 24 weeks.
- Value prior to the last dose administration at 76 weeks.

Thrombin generation:

- Peak thrombin generation (nM) prior to the last dose administration at 24 weeks.
- Peak thrombin generation (nM) prior to the last dose administration at 76 weeks.
- Endogenous thrombin potential (nM*min) prior to the last dose administration at 24 weeks.
- Endogenous thrombin potential (nM*min) prior to the last dose administration at 76 weeks.
- Velocity index (nM/min) prior to the last dose administration at 24 weeks.
- Velocity index (nM/min) prior to the last dose administration at 76 weeks.

The PD endpoints will be summarized and listed.

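### Thrombin generation samples during treatment carry no condition on recent rescue FVIII, which tilts the section 17.5 association between thrombin generation and ABR (minor)

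*Protocol*

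**What the plan says.** References are to protocol version 2.

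- **Sampling.** Section 8.5.1.1: "The Thrombin Generation Assay (TGA) will be performed at all visits, except visit 3". The only timing rule in the visible text for the visit 9 and 16 samples concerns the trial drug (Table 2-2, footnote h): "Patients must not treat themselves with concizumab until sampling has been performed". FVIII is not mentioned there.
- **Rescue FVIII.** Section 5.3.2 allows FVIII treatment of bleeds in the main, extension and follow-up parts, including self-treatment. Under Table 2-2, footnote l, FVIII activity is sampled only if reduced effect or an inhibitor is suspected.
- **Use of the values.** Section 17.6.4 lists absolute values as endpoints, for example "Peak thrombin generation (nM) prior to the last dose administration at 24 weeks", with ETP and velocity index, and the same at week 76. Section 17.5 plans "an analysis with individual steady state PK/PD assessments included as covariates in the negative" (the sentence goes on to name the ABR model of the primary analysis); the covariates include those three measures, and the stated aim is possible help with dose selection.
- **APTT.** Section 17.6.2 lists it among the safety endpoints: "Change from baseline of activated partial thromboplastin time (APTT) during 24 weeks from treatment onset".
- **FVIII intervals set elsewhere.** For the first dose, section 8.1.9.1 excludes "any FVIII treatment for prophylaxis or for treatment of a bleeding episode within a period of 48 hours prior to dosing". Section 8.1.7 has a rule for the screening visit: "sampling for FVIII activity at screening should be postponed if the patient has received FVIII within 96 hours". It applies only to patients whose files hold no FVIII level.

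**The concern.** Section 3.1.1 explains that FVIII deficiency is what makes the thrombin burst late and too weak. FVIII in the sample therefore acts on the quantity being measured, whatever concizumab is doing.

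If this were random it would only add noise. It is not random: a sample is affected when a bleed has just been treated, and treated bleeds are the outcome of the section 17.5 model. Frequent bleeders are more often sampled with FVIII on board, so higher thrombin generation becomes linked to higher ABR. That can mask a protective association in an analysis meant to inform dose choice. It would happen even if no patient were escalated.

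**Working it through.** There is no planned figure to reproduce; the check is of the text and of the scale.

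**1. Text.** No FVIII-free interval for thrombin generation or coagulation samples appears in 8.5.1.1, 8.5.2.5, the sections for visits 4 to 16, or the Table 2-2 footnotes. Flow chart Table 2-1 and the laboratory manual are not available, so a rule there cannot be excluded.

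**2. Residual FVIII.** Inputs: a rise of 2 IU/dl per IU/kg (8.3.1) and a single-dose ceiling of 50 IU/kg (note to Table 8-4). The half-life is not in the documents; 8 to 14 h is assumed. Residual = 2 × dose × 0.5^(t / half-life). Example at 48 h with a 12 h half-life: 2 × 50 × 0.5^4 = 6.25 IU/dl.

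| Hours after 50 IU/kg | 8 h | 10 h | 12 h | 14 h |
|---|---|---|---|---|
| 24 | 12.5 | 19.0 | 25.0 | 30.5 |
| 48 | 1.6 | 3.6 | 6.3 | 9.3 |
| 96 | 0.02 | 0.13 | 0.39 | 0.86 |

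Against the 1% severity limit in 6.2, this dose is still visible at 48 h and is not at 96 h.

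**3. Share of scheduled samples affected.** Chance that a treated bleed began within 96 h before a visit, taking one FVIII dose per bleed: 1 − exp(−ABR × 4 / 365.25).

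| ABR (17.1 and threshold) | Share | Of 30 patients | Share if treatment lasts 3 further days |
|---|---|---|---|
| 4 | 4.3% | 1.3 | 7.4% |
| 5.4 | 5.7% | 1.7 | 9.8% |
| 12 | 12.3% | 3.7 | 20.5% |

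The last column replaces 4 by 7 days; Table 8-4 foresees courses of 3 to 4 days or more for larger bleeds. Samples at visits triggered by bleeding (escalation visits, or procedures after stopping for lack of efficacy) are not counted and could add to the share.

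**4. Which patients.** Section 17.1 assumes ABR 4 and over-dispersion 6, that is, a mean of 2 bleeds in half a year. With a gamma-Poisson model, 1 + 2/k = 6 gives shape k = 0.4, and the gamma rate is 0.4/4 = 0.1. With w = 4/365.25 = 0.01095:

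- chance that a patient's sample is clean: (0.1 / 0.11095)^0.4 = 0.959
- mean ABR if clean: 0.4 / 0.11095 = 3.6
- mean ABR if affected: (4 − 0.9593 × 3.605) / 0.0407 = 13.3
- ratio: about 3.7
- chance that none of 30 patients is affected: 0.9593^30 = 0.29

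**5. Effect on the 17.5 slope.** Trials of 30 patients were simulated with these rates, thrombin generation otherwise unrelated to bleeding (SD 0.3 on the log scale), and affected samples multiplied by 1.5 or 2 (an assumption). A negative binomial regression then gives a spurious rate ratio of about 1.3 to 1.5 per doubling of thrombin generation. The standard error of the log rate ratio is about 0.65 to 0.70. The bias is therefore roughly log(1.3)/0.70 = 0.4 to log(1.5)/0.65 = 0.6 standard errors.

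**The case against.** The case for leaving the plan alone is substantial.

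- **Few samples, low stakes.** At the planned ABR one or two patients are affected at visit 9. Section 8.5.1.1 calls the assay exploratory, 17.6.4 only summarises and lists the values, and 17.5 is an additional analysis. This stands, and it sets the priority.
- **The data are already there.** Section 8.3.1 records dose, date and time of FVIII for each bleed, so values can be flagged, and exclusion rules are normal SAP content. This stands for the analysis step. A flag cannot, however, recover a clean week 24 sample; only a sampling rule in the protocol can.
- **The simulated slope is soft.** The 1.5- to 2-fold effect is not in the documents, and one multiplier for every affected sample ignores the decay towards 96 h. This stands.

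A reader might also infer more than the text supports:

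- **That former-prophylaxis FVIII reaches the PD endpoints or covariates.** Section 8.1.7 says "Patients on any previous FVIII prophylaxis can continue with this treatment until 48 hours before visit 2", but the thrombin generation endpoints are absolute values months later, and no change from baseline in thrombin generation is planned. Only the visit 2 baseline is exposed, which matters for APTT change from baseline.
- **That APTT feeds the ABR model.** It is a safety endpoint and is not among the 17.5 covariates. Dropping APTT values taken after FVIII would remove safety data on the combination.
- **That the protocol contradicts its own 96-hour rule.** That rule is conditional and protects the FVIII reading at screening. It is a precedent, not a standard for thrombin generation.
- **That a quarter or more of samples are affected.** The formula gives 28% at ABR 30, but 17 cites that level for on-demand treatment, not for concizumab.

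**Conclusion.** The gap is real and narrow. In the visible protocol, on-treatment thrombin generation samples have no condition on recent FVIII, and this biases the 17.5 association towards more thrombin going with more bleeding. About 4 to 6% of scheduled samples are affected at the planned ABR and about 12% at ABR 12, assuming one dose per bleed and a 96-hour window; longer courses raise this. The direction follows from the link between rescue and outcome and from the protocol's own account of FVIII. The size rests on an assumed half-life and an assumed FVIII effect on the assay, and it is well inside the standard error with 30 patients. The primary endpoint and both proof-of-concept criteria are untouched. Priority: minor.

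**What to change.** - **8.5.1.1.** State that if FVIII was given within a set interval (for example 96 h, borrowed from the screening rule), the visit 9 and 16 thrombin generation sample is taken later within the existing ±7-day window where possible, still before that day's concizumab. Visit 16 is meant to fall on the last day of concizumab, so there the visit would move as a whole within its window.
- **17.5 and 17.6.4.** Flag every thrombin generation sample from the recorded FVIII times. Leave flagged values out of the covariates and the main summaries, and list them separately. Because flagged patients are mostly frequent bleeders, also show the 17.5 model with all values.
- **17.6.2.** Keep all APTT values in the safety summary and only flag those taken soon after FVIII, including the visit 2 baseline, which may follow FVIII by only 48 h.

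The cost is one protocol sentence and an analysis flag. A few thrombin generation values are lost from the main summary where the sample cannot be moved. FVIII treatment does not change.

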8.5.1.2 Free TFPI

Free TFPI measures TFPI not bound to concizumab. This enzyme-linked immunosorbent assay (ELISA) test will be sampled for at all assessment visits.

The free TFPI ELISA assay is an enzyme immunoassay measuring levels of TFPI not bound to concizumab from Diagnostica Stago (named and referred to Asserachrom TOTAL TFPI) and will be used for PD assessments.

Free TFPI is included as a PD assessment.

Protocol
Trial ID:NN7415-4255
UTN:U1111-1179-3872
EudraCT no.:2016-000614-29

~~CONFIDENTIAL~~

Date:
Version:
Status:
Page:

05 May 2017 | **Novo Nordisk**
2
Final
64 of 124

8.5.2 Laboratory assessments for safety

8.5.2.1 Urinalysis

- pH
- Protein
- Glucose
- Bilirubin

This is a semi qualitative measurement which will be performed (locally) at the screening visit by the site by using the appropriate reagent strips for urinalysis. The results will be recorded in the eCRF.

Clinically significant findings must be recorded as:

- Normal or abnormal
 - if abnormal the investigator must:
 - record if the result is clinically significant? (Yes/No)
 - If observed before or at screening: record as concomitant illness (section [8.2.2](#))

8.5.2.2 Haematology

Haematology samples are to be sampled and analysed locally at all visits, except visit 3.

- Haemoglobin
- Erythrocytes (cell count)
- Thrombocytes (Platelet count)
- Leucocytes (cell count)
- Differential leucocytes cell count
 - Lymphocytes
 - Monocytes
 - Neutrophils
 - Eosinophils
 - Basophils

The investigator must evaluate the results and record the outcome as:

- Normal or abnormal
- If abnormal the investigator must:
 - Specify the abnormality
 - Record if the result is clinically significant (Yes/No)
 - If observed before or at screening: record as concomitant illness (section [8.2.2](#))
 - If observed after screening: report an AE/SAE (section [12](#))

Protocol
Trial ID:NN7415-4255
UTN:U1111-1179-3872
EudraCT no.:2016-000614-29

~~CONFIDENTIAL~~

Date:
Version:
Status:
Page:

05 May 2017 | **Novo Nordisk**
2
Final
65 of 124

Haematology results are to be entered into the eCRF.

8.5.2.3 Biochemistry

- Creatinine
- Albumin
- Bilirubin; total, direct and indirect)
- Aspartate aminotransferase (AST)
- Alanine aminotransferase (ALT)
- Gamma glutamyltransferase (GGT)
- Alkaline phosphatase
- C-reactive protein (CRP)

The investigator must evaluate the results and record the outcome as:

- Normal or abnormal
- If abnormal the investigator must:
 - Specify the abnormality
 - Record if the result is clinically significant (Yes/No)
 - If observed before or at screening: record as concomitant illness (section [8.2.2](#))
 - If observed after screening: report an AE/SAE (section [12](#))

8.5.2.4 FVIII activity

- FVIII activity (IU/ml)

